### Subjects

Table 1. Experimental Design

Clinical Assessment	Phase			
	Baseline	Randomization	Treatment	Post-treatment
	Week 1	End of Week 1	Wk 2 → Wk 6	Wk 7
Telephone Screen	WM Task		rTMS	WM Task

[figure not shown]

Figure 2. Scalp topography of control-related gamma oscillation power deficits in schizophrenia group compared to a healthy comparison group during the delay period of cognitive control task. Right frontal EEG leads show the most prominent deficits in schizophrenia. Left and right panels show superior and right lateral views respectively. From Minzenberg et al. [17].

Office Evaluations (SCID)	EEG Functional Status	[rTMS, Sham]	Sham	EEG Functional Status
---------------------------	-----------------------	--------------	------	-----------------------

A total of 24 subjects (12 rTMS and 12 sham) with SZ or SAD between the ages of 18 and 55 will be studied. Veterans will be recruited from a variety of sources including VAPHCS mental health clinics. We will consult with our system's Office of Data Analytics to identify potential subjects. We have already identified 366 veterans within the VAPAHCS population meeting the inclusion/exclusion criteria. We will work with this office to identify these veterans' VA clinicians who will assist in recruitment efforts. The study will be open to both men and women, regardless of race and ethnic origin. Details of demographics of the local VA population can be found in pg. 1 of the Human Subjects section.

Table 2. Inclusion and Exclusion Criteria

Exclusion Criteria	Inclusion Criteria
1) Pregnant or lactating female	1) Age 18-55 years
2) History of prior adverse reaction to TMS	2) SCID confirmed diagnosis of SZ or SAD
3) On medications known to significantly lower seizure threshold, e.g. clozapine, chlorpromazine, bupropion, clomipramine [21]	3) Stable medication regimen (no change in dose or agents within the 4 weeks prior to study entry and throughout the duration of the study)
4) History of seizures or conditions known to substantially increase risk for seizures	4) Stable social environment and housing to enable regular attendance at clinic visits
7) Implants or medical devices incompatible with TMS	5) Ability to undergo cognitive testing, EEG scans and rTMS
8) Acute or unstable chronic illness that would affect participation or compliance with study procedures, e.g. unstable angina	6) IQ > 80 (WASI full scale score)

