## Statistical Analysis

**Hypothesis Testing, Aim 1 - Subjects receiving rTMS will show improvements in a) WM performance, and b) occupational/role functioning compared to subjects receiving sham treatment:** Change scores (post-TMS vs. pre-TMS) for WM performance accuracy ( $\Delta$ WM Acc) and Global Functioning ( $\Delta$ GF) will serve as dependent measures for testing the hypothesis that rTMS improves cognition and functioning, respectively. The hypothesis will be supported if we find greater  $\Delta$ WM or  $\Delta$ GF in the active compared to the sham rTMS treated groups. We will use independent samples t-tests and two-sided tests for significance testing, with an alpha level of 0.05. However, given the limited scope of the SPiRE award, our primary goal is not on finding statistically significant differences but rather on determining the directionality of changes and the effect sizes of treatment effects. These data will be critical for determining if there is preliminary evidence that could support proposals for future larger scale studies.

**Hypothesis Testing, Aim 2 - Subjects receiving active treatment compared to those receiving sham treatment will show a) increased cognition associated gamma oscillation power, and b) an associated improvement in task performance:** Hypothesis 2 will be supported if we find significantly greater  $\Delta$ gamma in the active rTMS compared to the sham treated group. In addition, in the active rTMS treated group, we will conduct Pearson's bivariate correlation between  $\Delta$ gamma and  $\Delta$ WM. A positive correlation between these variables will support the hypothesis that rTMS improves cognition by increasing gamma oscillations. We will explore the possibility that pre-treatment gamma predicts rTMS responsiveness. We will evaluate this possibility by conducting a median split analysis in which subjects will be binned by their baseline gamma levels. We predict that those in the lower half of the distribution will show higher  $\Delta$ gamma and  $\Delta$ WM.

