**Intent-to-treat:** We will conduct a modified ITT analysis for hypothesis testing. We will use a modified ITT, which includes only subjects with outcome data, e.g. cognitive performance and EEG at the end of treatment [43], since good proxy measures cannot be imputed. To minimize missing data, we will acquire cognitive performance and EEG within one week of their last TMS session, including those intending to drop out. We will supplement this analysis with a per protocol analysis in which only subjects who completed all TMS treatments will be compared. This is done to determine, in a proof of concept manner, if TMS has the capacity to improve cognition in schizophrenia. We will include a careful examination of whether bias has been introduced due to dropout by determining if there is greater dropout in the treatment group and if significant differences exist in

major demographic and clinical variables of individuals who have dropped out compared to those who have not. We will correct for any significant differences using covariates in our statistical models.

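### The dropout-bias check is not split by arm, so losses that offset between active and sham can pass unnoticed

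*Combined protocol and SAP*

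**What the plan says.** All of the following is in the Statistical Analysis section.

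- **Outcome and test (Aim 1).** The dependent measures are "Change scores (post-TMS vs. pre-TMS) for WM performance accuracy" and the corresponding change in Global Functioning, compared between active and sham. "We will use independent samples t-tests and two-sided tests for significance testing, with an alpha level of 0.05". No baseline covariate is named.
- **Analysis sets (Intent-to-treat paragraph).** The main analysis is a "modified ITT, which includes only subjects with outcome data". It is supplemented by a "per protocol analysis in which only subjects who completed all TMS treatments will be compared". To limit missing data, subjects are to be tested within a week of their final session, and this extends to those who intend to leave.
- **Bias check (same paragraph).** It has two parts. One is "determining if there is greater dropout in the treatment group". The other asks whether there are significant differences in "major demographic and clinical variables of individuals who have dropped out compared to those who have not". Significant differences are then to be handled by adding covariates.

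The text does not say that the second comparison pools the arms. That is the plain reading, because no split by arm and no arm-by-dropout comparison is named. Nor is any comparison of active with sham among the subjects analysed.

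**The concern.** Attrition biases an active-minus-sham contrast when different kinds of subjects are lost from the two arms. Comparing all dropouts with all non-dropouts answers another question: whether those who leave are typical of the whole sample. The two questions can have opposite answers. Offsetting losses can look harmless when pooled although the arms have drifted apart. Similar losses from both arms can look alarming although the arms remain balanced. Since covariate correction is tied to this check, it can be omitted or applied for the wrong reason.

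The classifier is also imprecise. Dropping out is not the same as being excluded from the modified ITT. A subject who leaves early but is tested is included. A subject who finishes treatment but has no usable outcome, for instance no usable EEG, is excluded from that endpoint. The check may therefore describe a different group from the one missing, and the missing group can change by endpoint.

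The plan gives its main goal as the direction and size of the treatment effect, to support larger studies. An unnoticed shift would feed directly into that estimate.

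**Working it through.** The documents give no dropout rate and no power calculation, so there is no figure of the plan's own to reproduce. The only design input is 12 subjects per arm (Subjects section). All loss patterns below are assumptions.

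**Set-up.** Take any baseline variable in SD units with mean 0 in each arm at randomisation. Let k subjects per arm be lost without outcome data, at +m SD in active and -m SD in sham. Those remaining have mean -mk/(12-k) in active and +mk/(12-k) in sham, so the analysed arms differ by 2mk/(12-k).

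**Illustrative worst case, k = 3, m = 1.**
- Active: 3 × (+1) + 9 × (-1/3) = 0. Sham: 3 × (-1) + 9 × (+1/3) = 0.
- Rate check: 3 against 3, no difference.
- Pooled dropouts: mean 0. Pooled non-dropouts: mean 0. Difference 0.
- Remaining nine per arm: -1/3 against +1/3, a gap of 0.67 SD.
- Arm-by-dropout contrast: (1 + 1/3) - (-1 - 1/3) = 2.67 SD.

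**Range.** With m = 1, k = 1, 2, 3, 4 gives 0.18, 0.40, 0.67, 1.00 SD. With k = 3, m = 0.5 gives 0.33 and m = 1.5 gives 1.00 SD.

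**Effect of testing those who leave.** If j of the 3 per arm are tested, each modified ITT arm mean has size (3 - j)/(9 + j), and the gap is twice that:
- j = 0: 2 × 3/9 = 0.67
- j = 1: 2 × 2/10 = 0.40
- j = 2: 2 × 1/11 = 0.18
- j = 3: 0

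The per-protocol gap stays at 0.67 throughout, because these subjects did not finish treatment.

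**Other loss patterns (point differences).**

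| Lost from active | Lost from sham | Pooled dropout minus non-dropout | Gap between remaining arms |
|---|---|---|---|
| 3 at +1 | 3 at -1 | 0 | 0.67 |
| 3 at +1 | none | 1 - (-3/21) = 1.14 | 0.33 |
| 3 at +1 | 3 at the mean | 0.5 - (-3/18) = 0.67 | 0.33 |
| 3 at +1 | 3 at +1 | 1 - (-1/3) = 1.33 | 0 |

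The first row is missed, the middle two show, and the last is flagged although the arms are balanced.

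**Detection in the first pattern.** In simulation (40,000 runs at each of two within-group SDs, 0.82 and 1.0), the pooled comparison was significant in about 2% of runs, active against sham among those remaining in 27–37%, and the arm-by-dropout interaction in 77–91%.

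**Consequence for the treatment effect.** The shift in change score is the gap times the variable's correlation with change. For assumed correlations of 0.3 to 0.5 it is 0.67 × 0.3 = 0.20 to 0.67 × 0.5 = 0.33 SD. The standard error of a 9 against 9 difference is √(2/9) = 0.47 SD.

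**The case against.** A reader might infer that the planned check cannot reveal differential attrition at all, or that the analysed arms will differ by two thirds of an SD. The documents support neither. The pooled comparison reads zero only when opposite losses cancel; the one-sided patterns in the table give pooled gaps of 1.14 and 0.67 SD. The 0.67 SD gap needs 25% loss per arm, mirror-image selection at 1 SD and no testing of those who leave. None of these is in the documents, and the last runs against the plan's intention to test them. The only dropout experience reported is none among 27 subjects, in a different study (Preliminary Studies).

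Nor is the check the plan's sole protection, or the main analysis restricted to treatment completers. Testing those who leave is a safeguard in the same paragraph, and the modified ITT admits any subject with outcome data. For the per-protocol set, dropping out is close to the right classifier.

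The rate check is worded in one direction, but that does no work in the 3 against 3 example: a two-directional check would also read zero. Judging whether dropout is greater on active requires both arms' rates, so excess loss from sham would be visible even though the plan does not say it will be looked for.

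Finally, at this size a by-arm baseline comparison is imprecise. A 0.67 SD gap is 0.67/0.47 = 1.4 standard errors at 9 per arm and 0.67/0.41 = 1.6 at 12 per arm. It would arise by chance in about 16% and 10% of trials per variable, the latter with no dropout at all. Choosing covariates from such gaps would be unsound. The illustrative treatment-effect shift is itself below one standard error.

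These arguments limit the size of the problem and shape the remedy. They do not supply the missing by-arm comparison.

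**Conclusion.** The point holds as a defect in which groups are compared. The check is not aligned with the active-minus-sham contrast: it can miss offsetting losses and can flag harmless ones, and covariate correction depends on it. The size is illustrative only: up to 0.67 SD at baseline under the assumed worst case, less in the modified ITT to the extent that those who leave are tested, and unreduced per protocol. With assumed correlations of 0.3 to 0.5, this is 0.20 to 0.33 SD in the treatment contrast. The mismatch between dropping out and being excluded applies to the modified ITT and stands separately from that arithmetic. The documents do not show that such bias is likely here, only that the stated check could fail to reveal it. The change is worth making because it is cheap and because effect size is what the pilot is meant to deliver.

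**What to change.** Replace the two-part check in the Intent-to-treat paragraph with the following, for each endpoint and each analysis set:

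1. Tabulate included against not included by arm, with reasons, and read imbalance in either direction.
2. Compare included with not-included subjects on baseline variables within each arm, reported as an arm-by-inclusion contrast.
3. Report active-versus-sham standardised baseline differences among those analysed (WM accuracy, gamma, Global Functioning, BPRS, SANS, SAPS), descriptively and without tests.
4. Name any sensitivity-analysis covariates in advance, such as the baseline value of the outcome. Do not select them from the pooled dropout contrast or from observed imbalances.

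The cost is SAP wording and one extra table from baseline data already collected. Precision will be low at 9 to 12 per arm, so the table should inform interpretation and not act as a pass-or-fail test.

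### Covariate correction for dropout is triggered by significance tests that have little power in 24 subjects, leaving residual bias in the effect size the pilot is meant to deliver

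*Combined protocol and SAP*

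**What the plan says.** All of this is in the Statistical Analysis section of the combined protocol and SAP.

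- **Main model.** For Aim 1, change scores are compared between arms: "We will use independent samples t-tests", with "two-sided tests for significance testing, with an alpha level of 0.05". No covariate is named in advance. The same paragraph puts the direction and size of the effect ahead of statistical significance as the primary goal.
- **Analysis set.** The Intent-to-treat paragraph uses a modified set, "which includes only subjects with outcome data, e.g. cognitive performance and EEG at the end of treatment", and does not impute. A per-protocol analysis supplements it.
- **Dropout check.** Bias from dropout is examined in two ways: whether more subjects leave the active arm than the sham arm, and whether those who leave differ significantly from those who stay on the main demographic and clinical characteristics.
- **Correction.** "We will correct for any significant differences using covariates in our statistical models".

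The variables, their number, the tests and the significance threshold for the dropout check are not given. To limit missing data, outcomes are sought within a week of the last session, also from subjects who plan to leave.

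**The concern.** The correction depends on a pre-test. If the comparison of dropouts with non-dropouts is not significant, the unadjusted t-test stands; if some variable reaches significance, that variable enters the model. With 24 subjects and few dropouts, a non-significant result says almost nothing about whether bias is present. A significant result on one of many variables may be chance. Whether a variable differs significantly between dropouts and non-dropouts also says nothing about whether it predicts the outcome, and a covariate removes bias only if it does.

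The check on dropout rate has a further gap. A difference in rate between arms is not a subject-level variable, so no covariate can correct it.

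At stake is the treatment effect estimate. The plan intends to use it to decide whether larger studies are justified, so bias in it touches the main product of the trial.

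**Working it through.** The documents give no dropout rate or power figure for this check, so there is none to reproduce. The steps below compute how the rule behaves.

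**Inputs from the documents.** 24 subjects, 12 per arm (Subjects); unadjusted t-test, two-sided 0.05 (Aim 1).

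**Assumptions.** Two-sided 0.05 also for the baseline comparisons; 2 to 8 dropouts of 24; 5 to 10 variables tested.

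**1. Power to flag a variable that truly differs.** The groups are m dropouts and 24 − m others, not 12 and 12. For a true difference d in SD units, the noncentrality is d / √(1/m + 1/(24 − m)), with 22 df and critical value 2.074. For d = 0.8:

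| Dropouts v others | Noncentrality | Power |
|---|---|---|
| 2 v 22 | 0.8/√(1/2 + 1/22) = 1.08 | 18% |
| 4 v 20 | 0.8/√(1/4 + 1/20) = 1.46 | 29% |
| 6 v 18 | 0.8/√(1/6 + 1/18) = 1.70 | 37% |
| 8 v 16 | 0.8/√(1/8 + 1/16) = 1.85 | 42% |

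At 4 v 20, the difference detectable with 80% power is 1.6 SD.

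**2. Chance of adding an irrelevant covariate.** With k independent variables and no true differences this is 1 − 0.95^k: 23% for k = 5, 34% for k = 8, 40% for k = 10.

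**3. Power of the dropout-rate check, 12 v 12.** Exact power is the sum, over all pairs of dropout counts for which Fisher's test gives p ≤ 0.05, of the product of the two binomial probabilities.

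| True rates | Two-sided Fisher | One-sided Fisher |
|---|---|---|
| 30% v 10% | 9.5% | 19.7% |
| 40% v 10% | 23% | 39% |
| 50% v 10% | 42.5% | 60% |

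**4. Effect on the estimate (simulation, no true treatment effect).** Assumed: 8 independent baseline variables, one of them correlated 0.6 with the outcome. In the active arm the dropout probability is 25% at the mean of that variable, and its log-odds fall by 0.8 (moderate) or 1.5 (strong) per SD. In the sham arm it is 10%, unrelated to any variable. This gives about 5 dropouts. Runs with fewer than 2 dropouts, or fewer than 3 subjects left in an arm, are set aside.

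| | Moderate | Strong |
|---|---|---|
| Driving variable flagged | 13% | 28% |
| At least one irrelevant variable flagged | 31% | 30% |
| Bias, unadjusted (SD) | 0.12 | 0.20 |
| Bias, plan's rule (SD) | 0.11 | 0.16 |
| Bias, driving covariate fixed in advance (SD) | 0.00 | 0.00 |

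The SD of the estimate is about 0.46 under the rule and 0.39 with the fixed covariate.

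**5. Type I error.** With 5 dropouts at random, the final arm test under the rule rejects in 4.5% to 5.0% of runs. In the strong scenario of step 4 it rejects in about 6.5%, which reflects the bias in the estimate.

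**The case against.** Several points on the other side are sound.

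- **The test is still valid.** A reader might infer that data-driven covariates make the nominal t-test or interval inapplicable. The documents do not support that. The variables are selected by comparing dropouts with non-dropouts, not by looking at outcomes, and step 5 shows no material inflation under random dropout. Chance covariates cost degrees of freedom and little else.
- **Particular dropout counts.** A reader might infer that 4 of 12 v 0 of 12, or 6 of 12 v 1 of 12, would pass as not significant. That holds for two-sided Fisher (p = 0.093 and 0.069). It does not hold for one-sided Fisher (0.047 and 0.034) or the uncorrected chi-square (0.028 and 0.025). The plan names no test, and its question is directional: "by determining if there is greater dropout in the treatment group". The word significant is also attached to the demographic and clinical comparison rather than to the rate. Only the low power stands, at about 10% to 20% for 30% v 10%.
- **Mitigation.** Outcomes are sought from subjects who leave, and an earlier rTMS study by the group lost none of 27. That study had different primary goals, so it is weak evidence about a four-week course. If few outcomes are missing, the bias is small.
- **Pilot status.** The plan puts effect size ahead of significance. This does not answer the point, because the effect size is what the bias distorts.
- **Limits of the remedy.** Baseline adjustment does not help if dropout depends on the unobserved outcome. This stands and is reflected in the fix.

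**Conclusion.** The concern holds as a matter of residual bias and lost precision, not of invalid testing. The trigger would miss a 0.8 SD difference between dropouts and others in 58% to 82% of trials with 2 to 8 dropouts (100% minus 42% and 18%). In the assumed scenario the rule improves little on no adjustment: 0.11 v 0.12 SD of bias with moderate dependence, 0.16 v 0.20 with strong. That bias is about a quarter to a third of the estimate's own SD (0.11/0.46 = 0.24; 0.16/0.46 = 0.35). It is modest beside sampling error, but it is systematic and avoidable. The lost precision is relative to a model with a prognostic covariate fixed in advance (0.46 v 0.39).

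The dropout numbers, the number and independence of the variables, the tests and the simulation settings are all assumptions. That adjustment happens only on significance is inferred from the absence of any other stated correction. The bias arises only if the variable predicts outcome and its link to dropout differs between arms. The change should be made, but the trial does not fail without it.

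**What to change.** 1. Delete the significance trigger.
2. Fix the model in advance for each outcome (WM accuracy, GF, gamma): post-treatment value on arm plus the baseline value of the same outcome, whatever the dropout comparisons show. The change score may be kept as the dependent measure, since with baseline in the model the arm estimate is the same. Use the same model in the per-protocol analysis.
3. Report dropout by arm, and differences between dropouts and others, as estimates with intervals and not as a gate. Show subjects with no outcome separately, because those who leave but are still measured remain in the modified set.
4. State that this adjustment removes only the bias explained by the baseline value. Add a simple sensitivity analysis for dropout that depends on the unobserved outcome, for example giving missing subjects a range of worse outcomes and reporting where the conclusion changes.

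The cost is wording, one degree of freedom per model (22 to 21 with complete data) and a little more analysis. No new data are needed: Table 1 already schedules the WM task, EEG and functional status at baseline.
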